Study Protocol and Statistical Analysis Plan

Using Headphone Presentation to Investigate Compression Strategy
Modifications in Hearing Aids for Moderate-to-severe Hearing Loss –
ID# 365

August 3rd, 2021

NCT04882709

Using Headphone Presentation to Investigate Compression Strategy Modifications in Hearing Aids for Moderate-to-severe Hearing Loss – ID# 365

1 Objectives and hypotheses of the clinical investigation

1.1 Purpose of the clinical investigation claims for clinical performance, effectiveness or safety of the investigational device that are to be verified

The insight on general and individual preferences of fast and slow compression time constants generated in this study will be used to propose compression parameters for new hearing aids, which will be investigated in an in-person follow-up study.

1.2 Primary and Secondary Objectives

The primary objective of this study is to identify the most preferred compression setting for various acoustic scenes in experienced hearing aid users with moderate-to-severe hearing loss by subjectively rate recorded stimuli presented through headphones.

The secondary objective is to investigate potential benefit of a modifier for these compression settings by analyzing trends in individual preferences and their potential dependencies, such as hearing loss, acoustic scenes and previous amplification strategies.

2 Design of the clinical investigation

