2.2 Procedures

2.2.1 Investigation-related Procedure

The study is conducted remotely, so a potential participant's eligibility will be determined based on audiograms on file. If the study site doesn't have a participant's audiogram on file, the potential participant can request their HCP to release an audiogram to a study site.

After successful completion of the screening call, participants will sign the consent form and complete the demographic questionnaire over the phone. Afterwards, they will receive a package with a tablet and headphones and will get on another call with the researcher to conduct the subjective rating via an online sound survey tool.

The subjective rating will include rating of reverberation, sound source separation, sound source localization, overall preference ranking and an A/B test for preference. The stimuli consist of speech in quiet, speech in noise, reverberant speech, and music recorded with different hearing aids and hearing aid settings (hearing aids set to fast and slow compression settings, default

compression setting, a competitor's hearing aid and unaided), post-processed for headphone presentation and incorporated in an online sound survey.

3 Statistical design and analysis

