3.2.3 Secondary Endpoint Analysis

The study manager will analyze the collected data set in R Statistics after the data collection completed.

Subgroup analyses:

- Hearing loss: H_0 : There is no significant difference in sound quality ratings among all tested conditions depending on hearing loss degree.
- Acoustic scenes: H_0 : There is no significant difference in sound quality ratings among all tested conditions depending on acoustic scene.
- Previous amplification strategies: H_0 : There is no significant difference in sound quality ratings among all tested conditions depending on previous amplification strategy of participants.

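### The stated secondary tests detect varying margins between conditions, not a change in the best setting, so they do not answer whether a modifier would help

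*Combined protocol and SAP*

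**What the plan says.** The secondary objective in section 1.2 is to "investigate potential benefit of a modifier for these compression settings by analyzing trends in individual preferences and their potential dependencies". Section 3.2.3 (Secondary Endpoint Analysis) then gives three null hypotheses and no others:

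- Hearing loss: "There is no significant difference in sound quality ratings among all tested conditions depending on hearing loss degree".
- Scene: "There is no significant difference in sound quality ratings among all tested conditions depending on acoustic scene".
- Earlier amplification: "There is no significant difference in sound quality ratings among all tested conditions depending on previous amplification strategy of participants".

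The conditions are listed in section 2.2.1: fast, slow and default compression, plus "a competitor's hearing aid and unaided". That makes five, of which a modifier could choose among only the first three. The scenes are "speech in quiet, speech in noise, reverberant speech, and music".

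Section 2.2.1 also collects an "overall preference ranking and an A/B test for preference", and section 3.2.1 lists individual preferences as an additional analysis. Neither is given a method or a criterion. Section 1.1 says that what is learned will inform the compression parameters proposed for new hearing aids, which an in-person follow-up study will then examine.

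**The concern.** A modifier that selects a setting by scene or listener type raises the mean rating only if the best setting differs between levels. The nulls in section 3.2.3 are about something wider: whether differences among conditions vary with the factor at all. Two patterns make such a null false while leaving the modifier with nothing to do:

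1. One setting leads at every level, strongly at some and slightly at others.
2. The three selectable settings keep the same differences throughout, and only the unaided or competitor recording moves.

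Nothing in the plan separates these patterns from a true change of leader, and no section defines the gain of a modifier over the best single setting. A significant dependency could therefore be carried into the follow-up work as support for a modifier when the data give none at the level of means.

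**Working it through.** **The plan's own figure.** Section 3.2.1 gives an analysis population of 15-25. It cannot be reproduced, because section 3.1 rests on precedent and the documents give no alpha, power, SD or effect size. I use n = 15, 20 and 25.

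**Assumptions, none from the documents.** Two-sided alpha 0.05, normal ratings, and the SDs and margins stated below.

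**Definition.** Modifier gain = (mean over levels of the best setting's rating) − (mean rating of the best single setting). If one setting is best at every level, the two terms are equal and the gain is 0, whatever the SD.

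**1. Two scenes, same winner.** Per listener, the contrast is (fast − slow in scene 1) − (fast − slow in scene 2). With residual SD 1 per rating its SD is √4 = 2; any constant listener-by-setting effect cancels. The test is a one-sample t with n − 1 df and noncentrality Δ√n/2, where Δ is the difference in margin. For Δ = 1.5 (for example margins 1.7 and 0.2), noncentrality is 1.5 × √15/2 = 2.90 at n = 15.

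| Δ (SD) | n = 15 | n = 20 | n = 25 | Gain |
|---|---|---|---|---|
| 0.4 | 11% | 14% | 16% | 0 |
| 0.6 | 19% | 25% | 30% | 0 |
| 1.0 | 44% | 57% | 67% | 0 |
| 1.5 | 77% | 89% | 95% | 0 |

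**2. Two hearing-loss groups, same winner.** Here SD 1 refers to the within-listener difference between settings. Noncentrality is Δ/√(1/n₁ + 1/n₂) with n − 2 df and groups of 7/8, 10/10 and 12/13.

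| Margins in the two groups | n = 15 | n = 20 | n = 25 |
|---|---|---|---|
| 1.0 and 0.5 (same winner) | 15% | 19% | 22% |
| 1.5 and 0.5 (same winner) | 43% | 56% | 67% |
| 2.0 and 0.5 (same winner) | 76% | 89% | 95% |
| +0.5 and −0.5 (winner reverses) | 43% | 56% | 67% |

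The second and fourth rows are identical because the test sees only Δ = 1.0.

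**3. Four scenes, three settings, repeated-measures interaction F test** (4,000 simulated trials, residual SD 1).

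- One setting ahead by 0.4, 0.8, 1.2 and 1.6: deviations from the mean margin are −0.6, −0.2, +0.2, +0.6, with sum of squares 0.8. Rejection is 49/64/78%. Gain 0.
- A real reversal with margins −0.6, −0.2, +0.2, +0.6 has the same deviations. Rejection is 49/65/77%. Gain = (0 + 0 + 0.2 + 0.6)/4 − 0 = 0.2 SD.

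The noncentrality depends only on the deviations: n × 0.8 × 2/3 in both cases. The test cannot tell them apart.

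**4. Only the unaided recording moves.** Five conditions, slow ahead of fast, default and competitor by 0.5 in every scene, unaided at −0.4, −0.8, −1.2 and −1.6. Rejection is 45/61/74%, with gain 0. With no interaction, the same test rejects in 4.6% to 5.2% of runs, so it is correctly calibrated; the difficulty is the question it tests.

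**The case against.** Several points on the other side are sound.

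- **The primary objective covers scene.** Section 1.2 already seeks the preferred setting in various scenes. If one setting led in all of them, that result would argue against a scene modifier whatever the dependency test showed. This stands for scene, although section 3.2.2 names software rather than a method. It does not extend to hearing loss or earlier amplification.
- **The tests are not the whole route.** Ranking, A/B choice and individual preferences could show who prefers what. This stands, but no analysis or criterion is attached to them.
- **No decision rule.** A reader might infer that a significant test would lead the sponsor to adopt a modifier. The documents do not say so: the objective concerns potential benefit, and a follow-up study comes next.
- **Individuals.** A reader might also infer that a modifier supported this way would benefit nobody. Zero gain in scene or subgroup means does not exclude gain for individual listeners whose best setting differs. The tests in section 3.2.3 do not examine that either way.
- **Assumed effects.** The high rejection rates need large differences in margin; at 0.4 SD they are only 11/14/16%. Section 3.2.3 names no model, so the interaction reading is the natural one rather than a stated one.
- **A formal gain criterion would be weak here.** In simulations at n = 20 (four scenes, three settings, listener-by-setting SD 0.5, residual SD 1), requiring a bootstrap lower limit above zero detected a true 0.5 SD reversal in about 1-3% of runs, and a 0.8 SD reversal in about 30%. This stands and shapes the fix.

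**Conclusion.** The concern holds in a limited form. The only hypotheses stated for the secondary objective can be rejected with no change in the leading setting, and also by recordings that a modifier could never select. That is a matter of logic and needs no effect size. How often it would happen does depend on assumed values: for two scenes with the same winner and rating SD 1, from 19/25/30% at a 0.6 SD difference in margin to 77/89/95% at 1.5 SD (n = 15/20/25). The gap matters most for hearing loss and earlier amplification, where no other stated objective would reveal the leader by level. The consequence is a misleading lead into the follow-up study, not a final decision. The change should be made, but the study does not depend on it.

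**What to change.** In section 3.2.3, for the modifier question:

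1. Restrict the dependency analyses to fast, slow and default. Keep the all-condition tests as supportive.
2. For each level of scene, hearing loss and earlier amplification, report the pairwise setting contrasts with 95% intervals.
3. Cite a dependency as support for a modifier only where the leading setting changes between levels, not where only the margin changes.
4. Report the modifier gain over the best single setting as a descriptive estimate, not a pass/fail criterion. Choose the settings leave-one-listener-out, because the simple difference of maxima is biased upward: by about 0.08 rating SD at n = 20 when all settings are equal.

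The cost is SAP wording and a short R script on data already collected. There are two drawbacks. Fewer significant dependencies will count as support. With 15-25 listeners a moderate true reversal will often be inconclusive, especially for factors that vary between listeners, and the SAP should say so.

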2.1 General

2.1.1 Design Type

This is a randomized, double-blinded, cross-over, remote study with participants serving as self-controls and the current default compression setting as well as a competitor's hearing aid as comparator. An unaided recording will be provided as reference.

2.2 Procedures

2.2.1 Investigation-related Procedure

The study is conducted remotely, so a potential participant's eligibility will be determined based on audiograms on file. If the study site doesn't have a participant's audiogram on file, the potential participant can request their HCP to release an audiogram to a study site.

After successful completion of the screening call, participants will sign the consent form and complete the demographic questionnaire over the phone. Afterwards, they will receive a package with a tablet and headphones and will get on another call with the researcher to conduct the subjective rating via an online sound survey tool.

The subjective rating will include rating of reverberation, sound source separation, sound source localization, overall preference ranking and an A/B test for preference. The stimuli consist of speech in quiet, speech in noise, reverberant speech, and music recorded with different hearing aids and hearing aid settings (hearing aids set to fast and slow compression settings, default

compression setting, a competitor's hearing aid and unaided), post-processed for headphone presentation and incorporated in an online sound survey.

3 Statistical design and analysis

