3.1 Determination of Sample Size

We will recruit up to 28 participants, including up to 6 pilot participants. Previous research with subjective ratings has repeatedly shown that data collected with 15-25 participants can yield significant results. Since participants do not need to visit the research site, participants will be recruited from both locations as available.

Statistical criteria of termination of trial

If results for sound quality ratings are significant after 15 participants completed the rating, we will consider terminating the data collection.

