3.2 Planned Analyses

3.2.1 Datasets to be analyzed, analysis population

- Analysis population: 15-25 participants
- Evaluation group: rating per setting
- Data sets: subjective ratings
- Additional analyses:
 - individual preferences and their potential dependencies, such as hearing loss, acoustic scenes and previous amplification strategies
 - correction for repeated measures.

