3.2.2 Primary Endpoint Analysis

Automatic data analysis is available in the survey tool and will be used throughout the data collection for interim analysis. The study manager will analyze the collected data set in R Statistics after the data collection completed. Microsoft Excel may be used for arranging data and plotting data sets.

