3.2.4 Interim Analysis

Automatic data analysis is available in the survey tool and will be used throughout the data collection for interim analysis. Data will be adjusted for repeated measures.

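### The stopping rule and the only stated null hypotheses rest on an undefined outcome, sound quality ratings, and no primary endpoint is named, so the measure that decides early stopping is left open

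*Combined protocol and SAP*

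**What the plan says.** The primary objective (1.2) is to "identify the most preferred compression setting for various acoustic scenes in experienced hearing aid users". The secondary objective concerns individual preferences and how they depend on hearing loss, acoustic scene and previous amplification strategy.

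Section 2.2.1 gives the measures: "The subjective rating will include rating of reverberation, sound source separation, sound source localization, overall preference ranking and an A/B test for preference". That is three attribute ratings and two preference measures.

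The stopping rule in 3.1 reads: "If results for sound quality ratings are significant after 15 participants completed the rating, we will consider terminating the data collection". The three null hypotheses in 3.2.3 use the same outcome, for example: "There is no significant difference in sound quality ratings among all tested conditions depending on hearing loss degree".

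Section 3.2.2 is headed as the primary endpoint analysis, but gives only tools and timing: "Automatic data analysis is available in the survey tool and will be used throughout the data collection for interim analysis", and "The study manager will analyze the collected data set in R Statistics after the data collection completed". Section 3.2.4 adds: "Data will be adjusted for repeated measures". The planned size in 3.2.1 is "Analysis population: 15-25 participants".

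**The concern.** The term *sound quality ratings* decides whether collection may end early and carries every stated hypothesis, but it is not tied to any measure collected. The primary objective has no named endpoint, hypothesis, test or significance level. Because output is seen while data accrue, the deciding measure could be settled after results are known.

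Two consequences follow. The chance of a false positive rises with each measure and each look that may count. Collection may also end at 15, the bottom of the planned range, while preference is unresolved. Under 1.1, the preference findings are to be used to propose compression parameters for the follow-up study, so an error would carry forward into its settings.

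**Working it through.** **Text check**

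- *Sound quality ratings* occurs four times: once in the stopping rule (3.1) and once in each of the three null hypotheses (3.2.3). No section defines it.
- None of the five measures in 2.2.1 has that name.
- Section 3.2.2 names no primary endpoint, and no null hypothesis is stated for the primary objective.
- The same three factors (hearing loss, acoustic scenes, previous amplification strategies) appear in 1.2 and 3.2.1 attached to preferences, and in 3.2.3 attached to sound quality ratings. This suggests loose wording for the subjective or preference ratings. It does not choose between the ranking, the A/B test and the full set.

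**Inputs for the illustration**

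The plan gives no alpha, test, effect size or correlation, so it contains no power or error figure to reproduce.

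- From the plan: first decision point 15; range 15-25; up to 28 recruited, including up to 6 pilots.
- Derived: 28 − 6 = 22, if six pilots are left out of the analysis. The plan does not say whether they are.
- Assumed: two-sided 5% level; paired t test on normal data; correlation 0 to 0.8 between measures; effect of 0.5 SD; stopping whenever the criterion is met.

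**Step 1: several measures, one look**

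If the measures are independent, the risk is 1 − 0.95^m.

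- m = 3: 1 − 0.95³ = 0.143.
- m = 5: 1 − 0.95⁵ = 0.226.
- By simulation at correlation 0.8, these fall to about 10% and 13%.

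The range is therefore 10-23%.

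**Step 2: one measure, several looks (simulated under the null)**

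| Looks | p<0.05 at each | p<0.03 at each |
|---|---|---|
| 15 and 22 | 7.8% | 4.8% |
| 15 and 25 | 8.2% | 5.0% |
| 15 and 28 | 8.4% | 5.2% |
| every participant, 15 to 22 | 10.5% | not run |

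Repeat runs agree to within a few tenths of a percentage point. A Friedman test on ranks of three settings gives 7.7%, 7.9%, 8.3% and 10.7% at p<0.05. At p<0.03 with two looks it gives 4.3-4.8% for three to five conditions.

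**Step 3: stopping that loses a preference result**

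Suppose preference and the attributes all truly differ by 0.5 SD. The event that matters has three parts: an attribute is significant at 15, preference is not, and preference would have been significant had collection continued. The lower figure is for correlation 0.8, the higher for 0.

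| Final number | One attribute | Any of three attributes |
|---|---|---|
| 22 | 6-9% | 11-17% |
| 25 | 7-12% | 13-22% |

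**Step 4: power for a 0.5 SD paired difference**

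Power comes from the noncentral t distribution with n − 1 degrees of freedom and noncentrality 0.5√n.

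- Single 5% test: 44% at 15, 61% at 22, 67% at 25.
- p<0.03 at 15 and 22: 35% chance of stopping at 15, and about 55% power overall.

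**The case against.** **The term may simply mean preference.** The hypotheses in 3.2.3 mirror the secondary objective factor by factor, and 1.2 says that preference is found by subjective rating. This stands in part. A reader might infer that stopping rests on something other than the study's objective, and the documents do not support that: reading the term as the attribute ratings alone is the least natural, because 3.2.3 would then test something other than the objective it mirrors. Ambiguity remains even on the kind reading, since there are two preference measures and neither is chosen.

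**The repeated-measures adjustment may cover the looks.** In 3.2.4 it directly follows the sentence on interim analysis. Its ordinary meaning is correlation among ratings from one participant, and nothing extends it to repeated looks or several outcomes. If the sponsor did intend a wider correction, the risks in step 2 would not apply as shown.

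**Stopping is discretionary.** Section 3.1 commits only to considering it. The figures assume that the criterion is always acted on, so they show what the rule permits, not what will happen.

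**The harm from stopping on another measure is easily overstated.** A reader might count every case at 15 where an attribute is significant and preference is not: 11-25% for one attribute, 20-46% for any of three. That count includes cases which continuing would not resolve, so step 3 gives the relevant size.

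**This is early-stage work.** The results propose parameters for an in-person follow-up study, which limits the harm.

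**Conclusion.** The concern holds in this form: the outcome used for stopping and for the stated hypotheses is undefined, no primary endpoint is named, and as written collection can end at 15 on whichever measure is significant. This rests on the text and needs no calculation.

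At an assumed 5% level, with the criterion always acted on, false-positive risk is about 8% for one measure tested at 15 and again at 22-28. It is about 10% if that measure is tested after every participant from 15 to 22, and 10-23% if any of three to five measures counts at one look. If preference and attributes all differ by 0.5 SD, the chance of stopping on an attribute and losing a preference result that 22 participants would have shown is 6-9% for one attribute, or 11-17% for any of three.

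The documents do not show that the sponsor intends to stop on a measure unrelated to preference. The point should be fixed before data are seen, but the follow-up study keeps it short of critical.

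**What to change.** - **3.2.2:** name one preference measure, already collected, as the single primary outcome. The overall preference ranking with the A/B test as supportive is one option. The choice is the sponsor's, but must be fixed before data are seen.
- **Hypothesis:** state the primary null hypothesis over named conditions, saying whether the competitor device, a comparator in 2.1.1, is included. State whether the deciding test is one overall setting effect, or is made per scene with a multiplicity correction across the four scenes, so that it matches the objective in 1.2.
- **3.1 and 3.2.3:** use the same measure. Otherwise define *sound quality ratings* in 2.2.1 and state that it cannot trigger stopping.
- **Attributes:** make the reverberation, separation and localization ratings secondary.
- **Looks:** fix them in advance at 15 and the final number, and require p<0.03 for the deciding test at both (about 5% overall). Use other running output only for data checks.

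**Cost.** Wording changes in four sections, plus one data export and R run at 15 if the survey tool cannot do the test. No new data are needed. Attribute ratings can no longer end collection. An overall test can miss preferences that reverse between scenes, while per-scene tests pay for the correction. For a 0.5 SD paired difference, the chance of stopping at 15 falls from 44% to 35%, and power with looks at 15 and 22 is about 55%, against 61% for a single 5% test at 22.
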